12 SAFETY MONITORING PLAN

Table 2 Safety Monitoring Plan

Risks associated with trial interventions	
■ LOW = Comparable to the risk of standard medical care	
MODERATE ■ Somewhat higher than the risk of standard medical care	
☐ HIGH	
Justification: Briefly justify the risk category selected and yo (where the table is completed in detail the detail need not be summary should be given):	
The known risks and benefits to participants are well studied relevant SPCs. Although this protocol will study the use of these licensed indications there is no reason to believe that the risk is any higher in this population. These drugs will also be used in n are often prescribed, decreasing the risk of side effects occurring	e drugs outside of their in terms of AEs will be nuch lower doses than

related intervent	e the key risks to therapeutic ions you plan to in this trial?	How will these risks be minimised?			
IMP	Body system/Hazard	Activity	Frequency		
Amitriptyline, loperamide and ondansetron	Contraindication s to IMP	All study medications have a number of contraindications listed in the SPCs. Participants with these contraindications will be excluded from trial entry through the eligibility criteria/screening process.	Eligibility assessment		
	Interaction	All study medications have a number of interactions listed in the SPCs. Clinicians are advised to consider interactions prior to trial entry.	Eligibility assessment		
		Participants will be asked to inform the research nurse if they begin any new treatments whilst on the study.			
	Pregnancy	The SPCs for amitriptyline and ondansetron state that pregnancy is not recommended, The SPC for loperamide states that pregnancy is not advisable. Therefore patients who are pregnant, or planning to get pregnant, are excluded from the study and a pregnancy test will be administered to all women of child-bearing potential prior to study entry. This is over and above standard of care where pregnancy testing is not performed as the risks associated with these medications, and the doses used in this study, are considered low (see appendix 1 for further information). Patients will be advised not to become pregnant during the course of the trial and to advise the study team if they think they are	Eligibility assessment		
	Compliance with treatment (medication will be taken by	Participants will be given instructions to take home to provide details of how each treatment should be taken.	Throughout treatment		

	participants at home)		Prior to entering the trial and before the start of treatment
		Participants will receive telephone calls from research nurses to support dose titration and will have an optional review with a clinician at 4 weeks to discuss any concerns.	Throughout treatment
		Participants will also be given a diary card to record the number of tablets they have taken each day.	
	Allergic reaction	Participants with known allergies to amitriptyline, loperamide, and ondansetron will be excluded from the trial.	Eligibility assessment
Amitriptyline	Deliberate overdose/suicide attempt	Participants will be screened for suicidal ideation at screening and at baseline. We will also have a protocol in place to guide study nurses to notify the patient's GP in order to request urgent review (or other appropriate steps), in the event that someone with active suicidal ideation is identified, either at initial screening, or later interim screening checks, and prior to dispensing any drug prescriptions. We are prescribing a very low daily dose, and the sequential dispensing means that participants will only have a very limited total amount of drug that they can access. Patients already currently prescribed a TCA for the treatment of depression will be excluded.	Eligibility assess ment and at baseline prior to randomi sation
Loperamid e	Toxic megacolo n	During eligibility screening the blood and stool sample tests will confirm that there is no active inflammation present in the colon. In the event of clinical uncertainty regarding the stability of the patient's UC, a flexible	Eligibility assess ment and through out

· · · · · · · · · · · · · · · · · · ·	
sigmoidoscopy may be performed	treatme
at the discretion of the treating	nt
physician. In this situation, an	
endoscopic mayo score of ≤1 at	
flexible sigmoidoscopy will confirm	
the patient's eligibility for inclusion	
into the trial.	
Participants will be informed about	
the risks of developing toxic	
megacolon and will be given	
instructions on what to do if they	
begin to develop symptoms.	
Constipation is being	
monitored as an AE of	
special interest.	

Outline any other processes that have been put in place to mitigate risks to participant safety (e.g. IDMC, independent data review,...)

A DMEC will be convened for the trial, who will meet on an annual basis and will review interim unblinded safety information for the trial, as agreed by the committee at their initial meeting. Safety information will be reviewed at least 6-monthly whilst participants remain on treatment. Full interim reports will be presented to the DMEC, in confidence, annually. The DMEC will, in light of these reports, have the authority to recommend trial closure to the TSC should they have concerns over the safety or ethics of the trial. The TSC have the authority to recommend appropriate action including amendments to, or closure of, the trial at any time.

Participant data will be entered on to a validated database and monitored for completeness and quality by the CTRU. Missing data will be chased until it is received, confirmed as not available, or the trial is at analysis. Validation checks will be incorporated into the trial database to verify the data, and discrepancy reports will be generated for resolution by the trial site. Priority validations will be incorporated to ensure that any discrepancies related to participant rights, or the safety of participants, are expedited to sites for resolution.

13 STATISTICAL CONSIDERATIONS

13.1 Sample Size and Power Considerations

13.1.1 Phase 2

In the phase 2 period of the trial, a total of 396 participants will be recruited, 66 participants per intervention arm and 132 to the control group. This provides 90% power to detect an absolute difference of 17% (50% intervention, 33% control, odds ratio >2) in the proportion achieving improvement in discomfort from diarrhoea on the GSRS-IBS at 8 weeks, [26] with a 1-sided 20% significance level, assuming 10% of participants are lost to follow-up.

An absolute difference of 17% equates to a number needed to treat of 6. The IBS literature demonstrates consistently that therapies with a number needed to treat around this level are usually taken up in clinical practice, whereas there is often less enthusiasm for those with more modest effectiveness and a higher number needed to treat. This is a similar minimum clinically important difference to that we have stipulated in a trial in IBS, the EME-funded TRITON trial of ondansetron (15/74/01).

It is recommended that in a trial comparing one control group to several intervention arms, allocation should be in the ratio 1 to each intervention arm and the square root of the number of intervention arms to the control group, in order to maximise efficiency (smallest sample size for a given power). [35] In this case the ratio is 1:1:1:1:2.

13.1.2 Phase 3

If two interventions are carried forward from phase 2, a total of 491 participants are required: an additional 38 participants per intervention arm, and a further 19 participants in the control group (ratio 2:2:1). This will provide 90% power to detect a 16-point difference in the IBD-Q at 6 months, with 2-sided 2.5% significance, assuming an extra 10% of participants are lost to follow-up, and a standard deviation (SD) of 32. [36, 37] The final allocation ratio is 5:5:7 across both phases.

If only one intervention is carried forward from phase 2, a total of 426 participants are required: an extra 20 participants recruited to that intervention arm, and an extra 10 participants recruited to the control group (ratio 2:1). Again, this gives 90% power to detect a 16-point difference in the IBD-Q at 6 months, with 2-sided 5% significance, assuming an extra 10% lost to follow-up, and a SD of 32. [36, 37] The final allocation ratio is 5:8 across both phases.

The trial is powered to detect a 16-point difference in the IBD-Q at 6 months to assess overall clinical effectiveness. Studies have shown that a within-patient increase in IBD-Q score of between 16 and 32 points constitutes the lower and upper bounds of a clinically meaningful improvement in quality of life. [38, 39] The lowest point on this range represents the minimum clinically meaningful difference in disease specific quality of life at 6 months.

13.2 Endpoints

13.2.1 Primary Endpoint, Phase 2 - Improvement in Diarrhoea Symptoms at 8 Weeks Post-randomisation

Improvement in diarrhoea will be defined as scoring ≤2 on the diarrhoea subscale of the GSRS-IBS, [26] indicating minor discomfort from diarrhoea or less. The GSRS-IBS is a validated questionnaire, used widely in trials of medical therapies in gastrointestinal diseases. [26] It is a 13-item self-administered questionnaire measuring the presence and severity of gastrointestinal symptoms, which are measured on a 7-point Likert scale, defined by descriptive anchors (no discomfort at all; minor discomfort; mild discomfort; moderate

discomfort; moderately severe discomfort; severe discomfort; or very severe discomfort). The higher the scores, the more pronounced the symptoms.

13.2.2 Primary Endpoint, Phase 3 – Total IBD-Q Score at 6 Months Post-randomisation

The IBD-Q is a validated questionnaire, designed to measure disease-specific quality of life in people with inflammatory bowel disease. [27] The questionnaire has 32 items, which are grouped into four domains: bowel symptoms (10 items), systemic symptoms (five items), emotional factors (12 items), and social factors (five items). Each item is scored on a 7-point Likert scale, ranging from 1 (worst of health) to 7 (best of health). The total IBD-Q score therefore ranges from 32 to 224, with higher scores reflecting better quality of life.

13.2.3 Secondary Outcome Measures (at 8 Weeks and 6 Months Post-randomisation)

13.2.3.1 Loose Stools, Diarrhoea, Urgency, and Abdominal Pain

The GSRS-IBS, [26] which is described above, will be used to assess the effect of the various interventions on discomfort from loose stools, urgency, discomfort from diarrhoea and abdominal pain at both 8 weeks and 6 months.

13.2.3.2 Disease Activity (Escalation of Medical Therapy, Need for Surgery, CRP, and FC)

Data concerning need for either escalation of medical therapy for UC or surgery will be collected as a binary measure by research nurses from patient records at each participating centre at 8 weeks and 6 months, using a standardised CRF, which will be supplemented by patient questionnaires collecting these data. Participants will also provide blood for CRP (measured in mg/L) and stool for FC (measured in mcg/g) at 6 months only, which will both be collected as continuous measures.

13.2.3.3 Mood

The HADS is a well-validated, commonly used, self-report instrument for detecting anxiety and depression in people with medical illnesses. [28] It consists of a total of seven items measuring anxiety, and seven measuring depression, scored from 0 to 3, with a total score of 21 for each. Higher scores indicate more severe anxiety or depression.

13.3 Data Analysis

13.3.1 General Considerations

Statistical analysis is the responsibility of the CTRU statistician. The detailed statistical analysis plan (SAP) will be written in accordance with current CTRU standard operating procedures. It will be will be finalised and agreed by appropriate members of the trial team (trial and supervising statistician, the CI, the CTRU lead methodologist, project delivery lead, trial manager) before any analyses are undertaken. Any changes to the final analysis plan and reasons for change will be documented. Any deviation(s) from the final statistical plan in the final analysis will be described, and justification given, in the final report.

Analysis will take place in three stages, for the internal pilot, the phase 2 period, and the phase 3 period. The second of these is a formal interim analysis at which effectiveness on a single outcome (improvement in diarrhoea) will be analysed to determine which of the treatment groups will be carried forward into the phase 3 period of the trial.

13.3.2 Timing of Analyses

The recruitment progression criterion in the internal pilot will be assessed after 6 months of recruitment; rates of treatment withdrawal, adherence to a low FODMAP diet, and follow-up will be assessed after 12 months of recruitment.

The interim analysis of diarrhoea responders, to determine which treatments are carried through to the phase 3 period, will occur when all participants recruited during the phase 2 period have completed their 8-week follow-up data.

The final analysis will take place when all participants in the remaining treatment arms complete follow-up at 6 months, and after the database has been cleaned and locked.

13.3.3 Analysis Populations

Analyses will be on the ITT population, which will include all randomised participants, analysed according to the study arm to which they were randomised, irrespective of adherence to treatment. A per protocol analysis of the primary outcome will also be conducted, based on pre-defined criteria associated with intervention adherence.

13.3.4 Analysis of Internal Pilot

Data from the internal pilot will be analysed initially using descriptive statistics to evaluate the progression criteria. Outcome data from participants in the internal pilot will be included in the main trial analyses.

13.3.5 Descriptive Statistics

Descriptive statistics will be presented for demographics and baseline data, endpoints, and safety data. Continuous variables will be summarised by mean, SD, median, minimum, and maximum, as well as interquartile range, if appropriate. Categorical variables will be summarised by frequencies and percentages. A CONSORT diagram will display the flow of participants through the trial. Baseline characteristics of those lost to follow-up will be compared with those not lost to follow-up to assess for bias, and to inform the methods for handling missing data in inferential analyses.

13.3.6 Phase 2 Analysis and Progression to Phase 3

At the end of the phase 2 period, the diarrhoea responder rates at 8 weeks will be compared between the control group and each of the intervention arms individually, in logistic regression models adjusted for the stratification factors. Results will be expressed as odds ratios, together with 80% confidence intervals and p-values. Intervention arms will only be carried forward to phase 3 if the p-value in comparison with the control group is <0.2. This will correspond to an odds ratio >2, or to an absolute difference in response rate of 17%, when compared with the control group, if the response rate in the control group is 33%. If more than two intervention arms achieve this difference, the observed response rates, as well as safety, will be taken into account to decide which treatment arms should progress.

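### Section 13.3.6 equates the p<0.2 progression criterion with an odds ratio above 2 or a 17-point difference, but p<0.2 is reached at about 6 points one-sided or 10 points two-sided

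*Protocol*

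**What the plan says.** Protocol section 13.1.1 sets the phase 2 size at "66 participants per intervention arm and 132 to the control group". It describes the design effect as follows: "This provides 90% power to detect an absolute difference of 17% (50% intervention, 33% control, odds ratio >2"; the level and loss are given as "with a 1-sided 20% significance level, assuming 10% of participants are lost to follow-up".

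Section 13.3.6 then gives the progression rule: "Intervention arms will only be carried forward to phase 3 if the p-value in comparison with the control group is <0.2". It does not say whether this p-value is one-sided or two-sided, and the results are to be reported with 80% confidence intervals. The next sentence interprets the rule: "This will correspond to an odds ratio >2, or to an absolute difference in response rate of 17%, when compared with the control group", on the condition that 33% of controls respond. The one after that reads: "If more than two intervention arms achieve this difference, the observed response rates, as well as safety, will be taken into account".

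**The concern.** The 17-point figure does two different jobs. In section 13.1.1 it is an assumed true difference, which the test should detect with high probability. In section 13.3.6 it is presented as the effect to which p<0.2 corresponds, that is, as a decision threshold. In a test with 90% power, the observed effect that just reaches significance must lie well below the true effect the test is powered for. Otherwise an arm with that true effect would miss the threshold about half the time.

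The statement sits inside the rule that selects arms for phase 3. It fixes the control rate, so it is a numerical claim that can be checked. The following sentence speaks of arms achieving this difference, and the only difference mentioned before it is the 17 points. An arm with an observed difference between the true p-value threshold and 17 points meets the stated rule but does not meet the gloss. Section 13.1.1 also links 17 points to a number needed to treat of 6, so a reader could believe that every arm taken forward had shown an effect of that size.

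**Working it through.** **Inputs.** From section 13.1.1: 66 per intervention arm, 132 control, 10% loss, 50% versus 33% response, one-sided 20% level, 90% power. Evaluable numbers: 66 × 0.9 = 59.4 and 132 × 0.9 = 118.8. Odds ratio: (0.50/0.50)/(0.33/0.67) = 2.03. From section 13.3.6: p<0.2, control response 33%.

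**1. The plan's own figure reproduces, one-sided.**
- Pooled rate: (59.4 × 0.50 + 118.8 × 0.33)/178.2 = 0.387.
- Null standard error: √[0.387 × 0.613 × (1/59.4 + 1/118.8)] = 0.0774.
- Standard error under the alternative: √(0.25/59.4 + 0.33 × 0.67/118.8) = 0.0779.
- One-sided power: Φ[(0.17 − 0.842 × 0.0774)/0.0779] = Φ(1.346) = 0.911, in line with the stated 90%.
- Two-sided power: Φ[(0.17 − 1.282 × 0.0774)/0.0779] = 0.818, which does not match.
- The log-odds-ratio formula returns the planned size if control is taken as one third and the odds ratio as exactly 2 (my assumption): (0.842 + 1.282)² × [1/0.25 + 1/(2 × 0.222)]/(ln 2)² = 58.6, rounded up to 59; 59/0.9 = 65.6, rounded up to 66.

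So 17 points is the powered alternative of a one-sided 20% test.

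**2. Observed difference at which p reaches 0.2.** Hold control at 0.33 and solve z = d/√[p̄(1 − p̄)(1/n₁ + 1/n₂)] for d, with z = 0.842 (one-sided) or 1.282 (two-sided).

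| Numbers | One-sided p=0.2 | Two-sided p=0.2 |
|---|---|---|
| 59.4 vs 118.8 | 6.4 points, OR 1.32 | 9.8 points, OR 1.52 |
| 66 vs 132 (no loss) | 6.1 points, OR 1.30 | 9.3 points, OR 1.49 |

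Check of the first cell: p̄ = 0.351, standard error 0.0759, 0.0638/0.0759 = 0.84. A Wald test on the log odds ratio gives the same thresholds to within 0.1 point.

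**3. The p-value at an observed 17 points.** z = 0.17/0.0774 = 2.20, so p is 0.014 one-sided or 0.028 two-sided (0.010 and 0.021 with no loss). This is far below 0.2.

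**4. How often each reading lets an arm qualify.** Exact binomial enumeration, 59 versus 119, control 33%:

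| Reading | True 50% (target) | True 33% (null) |
|---|---|---|
| One-sided p<0.2 | 91% | 20% |
| Two-sided p<0.2 | 82% | 10% |
| Observed difference at least 17 points | 51% | 1% |
| Observed OR above 2 | 53% | 2% |

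For an arm with exactly the target effect, 91% − 51% = 40% of trials would meet one-sided p<0.2 while showing less than 17 points.

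**5. The confidence interval.** A two-sided 80% interval excludes 1 when two-sided p<0.2. In the favourable direction that is one-sided p<0.1, which is stricter than the one-sided 0.2 of section 13.1.1. A one-sided 80% bound, or a two-sided 60% interval, matches one-sided p<0.2.

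**The case against.** The strongest reply is that there is only one rule. Only the p-value sentence in section 13.3.6 is worded as a condition, the 17-point sentence is commentary on it, and section 13.1.1 shows where the figure comes from. A statistician would most likely apply p<0.2. This stands. A reader might infer that the protocol sets two conflicting gates, but nothing in the text says that an arm must show 17 points.

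A reader might also take the last sentence to make 17 points the criterion for choosing among arms. It does not. The choice rests on observed response rates and safety; the difference only determines when that choice is needed, namely when more than two arms qualify. It could be loose wording for meeting the p-value criterion. Even so, the trigger is ambiguous. If three arms showed 8, 12 and 18 points, one-sided p would be about 0.15, 0.06 and 0.01. All three would meet one-sided p<0.2, yet only one would have achieved the 17 points.

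Third, the stated power is not lost under the explicit rule. Read one-sided, it gives about 91%. The drop to about 51% arises only if someone enforces an observed 17 points.

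Finally, the thresholds come from an unadjusted test, while the plan adjusts for stratification factors and may multiply impute missing primary outcomes. That moves them slightly. With no loss at all they are 6.1 and 9.3 points, so neither adjustment nor imputation could plausibly bring them near 17.

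**Conclusion.** The statement that p<0.2 corresponds to an odds ratio above 2 or to 17 points is wrong on the protocol's own figures. The observed threshold is about 6 points (OR about 1.3) one-sided or about 10 points (OR about 1.5) two-sided, so the stated figure is too large by a factor of about 2.7 (17/6.4) or 1.7 (17/9.8). This rests on 33% control response, about 59 versus 119 evaluable, and an unadjusted comparison.

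The consequence is a false gloss on a single explicit rule. It allows a second reading under which an arm with the target effect would qualify about 51% of the time instead of about 91%. It could also lead readers to credit every arm carried forward with a number needed to treat of 6, when a one-sided pass needs only about 6.4 points observed (1/0.064, about 16). Separately, the rule leaves its sidedness unstated beside 80% intervals, which conventionally match a two-sided p<0.2; that reading gives about 82%. Because the text sits in the arm-selection rule, it should be corrected before the phase 2 analysis.

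**What to change.** Three edits to section 13.3.6:

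1. State in the rule itself that the p-value is one-sided and must be below 0.2, matching section 13.1.1. Say how the 80% confidence interval relates to it: the lower limit of a two-sided 80% interval corresponds to one-sided p<0.1, whereas a one-sided 80% bound or a two-sided 60% interval matches the rule.
2. Replace the sentence on correspondence with: *17 points/OR 2 is the effect the phase is powered to detect; with about 59 vs 119 evaluable and 33% control response, one-sided p<0.2 is reached at an observed difference of approximately 6 percentage points (OR about 1.3), unadjusted.*
3. In the sentence on more than two arms, refer to arms that meet the p-value criterion instead of arms that achieve the difference.

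The cost is a few sentences of text. Sample size, allocation and analysis model do not change. The one drawback is presentational: the smallest observed effect that lets an arm progress is stated openly and looks more modest than 17 points.

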13.3.7 Primary Endpoint Analysis

The primary analysis in the phase 3 period will compare IBD-Q scores at 6 months between the control group and the intervention arms individually, in linear regression models adjusted for the stratification variables and baseline IBD-Q. Results will be expressed as point estimates, together with 95% or 97.5% confidence intervals (when there are one or two intervention arms, respectively), and p-values.

For the primary endpoints only, missing data will be multiply imputed, where appropriate. When questionnaires have missing items, scoring instructions specific to the questionnaires will be followed, or if no such instructions exist the summary scores will be calculated from the non-missing items, as long as at least half are non-missing.

Sensitivity analyses on a per-protocol population will test the robustness of the results.

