4.3 Phase 2 to Phase 3 Transition

Phase 2 will evaluate the short-term effectiveness of all active interventions, each compared with a control of standard first-line dietary advice at 8 weeks, in terms of improvement in diarrhoea, via the diarrhoea subscale of the GSRS-IBS. Analysis will be performed when sufficient patients have reported 8 week GSRS-IBS outcome data and a maximum of two of the interventions showing evidence of short-term effectiveness will continue to phase 3 to evaluate longer-term effectiveness in terms of improved disease-specific quality of life, via the IBD-Q at 6 months post-randomisation.

There will be a temporary halt to active recruitment of approximately 3-4 months after approximately 396 participants are recruited to phase 2, to allow for analysis prior to progression to phase 3. We expect to require 19 months of recruitment to recruit these first 396 patients, meaning that all data for the 8-week time point should be collected by month 21.

Figure 1 Summary of Trial Design

Trial Design

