6.8.2 Treatment Allocation

For both phase 2 and phase 3, randomisation will be via minimisation at the level of the individual, stratified according to:

- Centre;
- Degree of discomfort from diarrhoea (score ≥5) ;
- Extent of UC (left sided or extensive);
- Depression via HADS-Depression score (score ≥8).

Phase 2 randomisation: participants will be randomised in the ratio 1:1:1:1:2, with the larger group receiving the control intervention.

Phase 3 randomisation: participants will be randomised in the ratio 2:1, or 2:2:1, depending on the number of active interventions taken forward, with the smaller group receiving the control intervention.

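### The final IBD-Q model pools two phases with reversed allocation ratios but has no phase term, so an unexplained shift between phases would bias the treatment effect

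*Protocol*

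**What the plan says.** Protocol section 13.3.7 sets the primary phase 3 analysis: IBD-Q at 6 months, each intervention arm against control, "in linear regression models adjusted for the stratification variables and baseline IBD-Q". Section 6.8.2 gives the stratification variables, the same for both phases: centre, degree of discomfort from diarrhoea, extent of UC, and HADS-Depression. Phase, or recruitment period, is in neither list.

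Section 6.8.2 allocates 1:1:1:1:2 in phase 2, with control the larger group. In phase 3, "participants will be randomised in the ratio 2:1, or 2:2:1, depending on the number of active interventions taken forward", with control now the smaller group.

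Section 13.1 sizes the final comparison on both phases together:
- Phase 2: "66 participants per intervention arm and 132 to the control group".
- Phase 3 with two arms: "an additional 38 participants per intervention arm, and a further 19 participants in the control group (ratio 2:2:1"). "The final allocation ratio is 5:5:7 across both phases".
- Phase 3 with one arm: "an extra 20 participants recruited to that intervention arm, and an extra 10 participants recruited to the control group (ratio 2:1"). "The final allocation ratio is 5:8 across both phases".

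Section 4.3 separates the phases: "There will be a temporary halt to active recruitment of approximately 3-4 months", during which the phase 2 results decide which arms continue. Section 4.1 states that participants and those delivering the interventions are not blinded.

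**The concern.** Randomisation makes the arms comparable within each phase. It does not make a phase 2 participant comparable with a phase 3 participant. Because the ratio reverses, phase is associated with treatment by design: active participants are drawn more heavily from phase 3 than controls are. If 6-month IBD-Q differs between the phases for a reason the model does not capture, part of that difference is counted as treatment effect.

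Some shift is plausible. Recruitment stops for some months and then restarts, the outcome is self-reported, the trial is open, and phase 3 participants join a trial that offers only the interventions that were retained. At stake are the estimate and the type I error of the confirmatory comparison. The only sensitivity analysis named in section 13.3.7 is per-protocol, which would not reveal the problem.

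**Working it through.** **Inputs.** From section 13.1: phase 2 has 66 per active arm and 132 control; phase 3 adds 38 and 19 (two arms) or 20 and 10 (one arm). The target difference is 16 points, the SD is 32, and two-sided alpha is 2.5% (two arms) or 5% (one arm). Loss is 10% in phase 2 and an extra 10% in phase 3. I read this as cumulative, so retention is about 80%.

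**Reproducing the stated power.** Pooled information is n_a × n_c / (n_a + n_c), and SE = 32 / √(0.80 × information).
- Two arms, 104 v 151: information 61.6, SE 4.56. Power = Φ(16/4.56 − 2.241) = 89.8%.
- One arm, 86 v 142: information 53.6, SE 4.89. Power = Φ(16/4.89 − 1.960) = 90.5%.

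Both agree with the stated 90%. They are pooled calculations with no phase term.

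**Imbalance between phases.** In the pooled contrast, bias = (phase 3 share of active − phase 3 share of control) × residual shift.
- Two arms: 38/104 − 19/151 = 0.365 − 0.126 = 0.24.
- One arm: 20/86 − 10/142 = 0.233 − 0.070 = 0.16.

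**Consequence for assumed shifts.** The protocol gives no drift figure, so 2, 5 and 10 points are assumptions. They mean an additive shift common to all arms that remains after the planned covariates. Two-sided type I error = 1 − Φ(z − bias/SE) + Φ(−z − bias/SE), with the SEs above and no credit for baseline adjustment.

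| Residual shift | Two arms: bias | Two arms: type I error (nominal 2.5%) | One arm: bias | One arm: type I error (nominal 5%) |
|---|---|---|---|---|
| 2 points | 0.5 | 2.6% | 0.3 | 5.1% |
| 5 points | 1.2 | 3.0% | 0.8 | 5.3% |
| 10 points | 2.4 | 4.6% | 1.6 | 6.3% |

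If a 10-point shift ran against the active arm, the 16-point target would be detected with power 77% (two arms) or 84% (one arm).

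**Cost of a phase term.** With phase in the model, each comparison uses the information within phases, summed.
- Two arms: 66×132/198 + 38×19/57 = 44 + 12.7 = 56.7, which is 0.92 of 61.6. Power is 87.0% with pairwise fits, or 88.0% if both active arms and control are fitted in one model.
- One arm: 44 + 20×10/30 = 44 + 6.7 = 50.7, which is 0.946 of 53.6. Power is 88.9%.

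**Offset from baseline adjustment.** If baseline IBD-Q correlates with the 6-month score at r = 0.3 (assumed), the residual SD is 32 × √(1 − 0.09) = 30.5. Phase-adjusted power is then 90.1% (two arms, pairwise) and 91.6% (one arm).

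**What a phase term does not remove.** Suppose that in phase 3 expectation added 5 points in the active arm and took 5 from control (assumed).
- Pooled bias with two arms: 5 × 0.365 + 5 × 0.126 = 2.46.
- With a phase term, pairwise: 10 × 12.67/56.67 = 2.24.

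Most of that bias remains.

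**The case against.** Four objections have weight.

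**Only a residual shift counts.** A change in case mix is partly absorbed by baseline IBD-Q, centre, diarrhoea severity, extent and HADS-Depression, and the protocol sets out one set of eligibility criteria and stratification factors for both phases. A reader might infer that every difference between phases biases the result. The documents do not support that, and the claim is limited accordingly.

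**The size is unknown.** Ten points is 0.31 of the protocol's SD. At 2 points the error rates are close to nominal, and with one arm they stay close at 5 points. A reader might infer that the type I error of the two-arm test doubles. That needs a residual shift of about 10 points, for which the protocol offers no evidence.

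**The power is not wrong.** A reader might also infer that the 90% in section 13.1.2 is an error. The pooled calculation reproduces it, and the planned baseline adjustment would roughly pay for a phase term. If loss is 10% in total rather than cumulative, phase-adjusted power is 90.8% (two arms) and 92.2% (one arm) even without that credit.

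**The analysis plan could add phase.** It could, and section 13.3.1 defers detail to it. But section 13.3.7 names a covariate set, and an analysis plan that followed it as written would leave phase out. This objection lowers the severity but does not remove the point.

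**Conclusion.** The point holds as a should-fix. The protocol's primary model pools two phases with opposite allocation ratios and omits the variable that separates them. Any additive between-phase shift in 6-month IBD-Q that the planned covariates do not explain biases the treatment effect by 0.24 points per point of shift with two arms, or 0.16 with one.

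The multipliers follow directly from the protocol's numbers. The practical size rests on an assumed shift: small at 2 points, and at 10 points a bias of 2.4 against the 16-point target with two arms. The error rates further assume 80% retention, an SD of 32 and no gain from baseline adjustment.

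It would be too strong to say that a phase term restores the nominal error rate in every case. It does so for a shift common to all arms, but not for expectation effects that differ between active and control.

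**What to change.** In section 13.3.7, add phase (2 v 3) as a fixed covariate in the primary IBD-Q model. Do the same in its imputation model and in the other final analyses that pool both phases. Report the treatment effect separately by phase as a description, because the main effect of phase does not deal with effects that differ by arm. With 19 phase 3 controls at most, this should not be presented as a formal test.

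In section 13.1.2, the 90% can stand. Add a note that, with a phase term, it relies on the planned adjustment for baseline IBD-Q.

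The cost is one covariate and no new data. Information falls by about 8% (two arms, pairwise) or 5% (one arm). On the protocol's own formula at about 20% cumulative loss, power goes from 90% to about 87–88% (two arms) or from 91% to 89% (one arm), before credit for baseline adjustment. A baseline correlation of about 0.3 (assumed) brings it back to 90%. The change should be made before outcome data are seen.
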